5.2 General Concomitant Medication and Supportive Care Guidelines

Patients will have to adhere to a low iodine diet 5 days prior to the initiation of the lesional dosimetry process and continued until the completion of that process. For those patients who

will go on to receive therapeutic ^{131}I , they will need to be continued on the low iodine diet through 1 day after ^{131}I administration. For details of the suggested low iodine diet, please see [Appendix B](#).

5.3 Duration of Therapy

In the absence of treatment delays due to adverse event(s), treatment may continue until one of the following criteria applies:

1. Disease progression (however, Cohort A and B patients with evidence of clinical disease progression or RECIST v1.1 radiographic progression (such as on the ^{124}I PET/CTs or other scans) prior to the 6-month evaluation of the primary/secondary endpoints may be continued on treatment and the study if the treating physician deems it clinically reasonable),
2. Intercurrent illness that prevents further administration of treatment,
3. Unacceptable adverse event(s),
4. Patient decides to withdraw from the study,
5. General or specific changes in the patient's condition render the patient unacceptable for further treatment in the judgment of the investigator,
6. (For Cohort A and B patients) It is determined that a patient will not receive therapeutic ^{131}I and the treating physician determines that it is not clinically reasonable to continue with trametinib therapy alone or the patient does not want to continue with trametinib therapy alone,
7. For patients who do receive therapeutic ^{131}I , trametinib will be continued until 2 days after ^{131}I is administered. Patients will remain on study for tumor assessments that will be completed approximately 6 months after ^{131}I therapy. Safety monitoring for trametinib related toxicities will be continued until 30 days after last trametinib dose.
8. All study therapy has been completed as planned.

5.4 Duration of Follow Up

Adverse events will be followed for 30 days after the last dose of trametinib. Patients removed from study for unacceptable adverse event(s) will be followed until resolution or stabilization of the adverse event.

5.5 Criteria for Removal from Study

Patients will be removed from the study when criteria numbers 2-8 in [Section 5.3](#) apply or if the following criteria apply:

- Progression of disease on Cohort C,
- Progression of disease on Cohort A or B and the patient will not be continuing to Cohort C (exceptions to this for Cohorts A and B are detailed in the [Section 5.3](#)),
- The patient is started on another therapy for his/her thyroid cancer besides what is detailed as allowed in this protocol

The reason for study removal and the date the patient was removed must be documented in the Case Report Form.

6. DOSING DELAYS/DOSE MODIFICATIONS

6.1 Trametinib Dose Modifications

The table below outlines the dose levels to be used for any necessary trametinib dose modifications:

Dose Level	Trametinib Dose/Schedule
0	2 mg QD
-1	1.5 mg QD
-2	1 mg QD

A maximum of two trametinib dose level reductions are allowed. If a third dose level reduction is required, treatment will be permanently discontinued. In order to ensure that patients have taken trametinib for a minimum of 7 consecutive days, missed doses may be made up (as per [Section 5.1.1](#)) and study assessments/treatments appropriately rescheduled. If trametinib is missed for \geq 7 days or interruptions in trametinib dosing have occurred prior to whole body and blood dosimetry and ^{131}I (RAI) treatment, then having some or all of the doses made up and the study assessments/treatments appropriately rescheduled may be considered after discussion with the MSK Principal Investigator (this is not a requirement) (as per [Section 5.1.1](#)).

6.1.1 Trametinib Dose Modification for Toxicities Not Specified in Subsequent Sections

Trametinib Treatment Modification for Clinically Significant Toxicities Deemed Related to Trametinib (This section is not for specific AEs such as hypertension, rash, ejection fraction changes, pneumonitis, diarrhea, liver chemistry, QTc prolongation, or visual changes. Refer to other sections for these specific AEs).		
CTCAE v4 Grade	Management Guideline	Dose Modification
Grade 1	Monitor as clinically indicated.	Continue trametinib at current dose level.
Grade 2	Provide supportive care according to institutional standards	Continue trametinib at current dose level. If intolerable, interrupting treatment may be considered only after discussion with the Principal Investigator. For patients who have trametinib held for grade 2 toxicities, trametinib may be restarted at the same dose or with one level of dose reduction.

Trametinib Treatment Modification for Clinically Significant Toxicities Deemed Related to Trametinib		
(This section is not for specific AEs such as hypertension, rash, ejection fraction changes, pneumonitis, diarrhea, liver chemistry, QTc prolongation, or visual changes. Refer to other sections for these specific AEs).		

CTCAE v4 Grade	Management Guideline	Dose Modification
Grade 3		
 Interrupt treatment until resolution to grade 1 or baseline*. Upon resolution to baseline or grade 1, restart with one level of dose reduction*. If the Grade 3 toxicity recurs, interrupt trametinib. When toxicity resolves to Grade 1 or baseline, restart trametinib reduced by another dose level
Grade 4		Permanently discontinue trametinib.**

Trametinib should be discontinued if treatment delay is > 21 days due to toxicities. If the investigator concludes that continued trametinib will benefit a patient, the study chair (MSK PI) and CTEP Medical Monitor, may be consulted for the possibility of resuming trametinib, provided that toxicities have resolved to baseline or grade 1.

*For non-life threatening Grade 3 laboratory abnormalities, trametinib may be continued at the same dose without interruption if deemed appropriate by the MSK Principal Investigator.

**For Grade 4 lymphopenia, study treatment may be continued at the same dose level without interruption based upon investigator judgment.

6.1.2 Trametinib Dose Modification for Rash

Rash is a frequent AE observed in patients receiving trametinib (Investigator's Brochure, 2012a). Recommendations for supportive care and guidelines for dose modifications for rash are based on experience with other MEK inhibitors and EGFR inhibitors (Balagula *et al.*, 2010; Lacouture *et al.*, 2011).

The institutional standards for the management of skin-related AEs can differ from these guidelines. In this case, best clinical judgment should be applied and a consultation with the MSK Principal Investigator or the CTEP Medical Monitor, through MSK, may be required.

Guidelines for Supportive Care of Rash	
Type of Care	Action
Prevention/Prophylaxis ^a	
 Avoid unnecessary exposure to sunlight. Apply broad-spectrum sunscreen (containing titanium dioxide or zinc oxide) with a skin protection factor (SPF) ≥ 15 at least twice daily when exposed to sunlight. Use thick, alcohol-free emollient cream (e.g., glycerine and cetomacrogol cream) on dry areas of the body at least twice daily. Use mild-strength topical steroid (hydrocortisone 1% cream) or topical antibiotic (e.g., clindamycin) (should be applied at least twice daily starting on Day 1 of study treatment to areas such as face, chest, and upper back) or oral antibiotics (e.g., doxycycline 100 mg BID, minocycline 100 mg BID).

Guidelines for Supportive Care of Rash	
Type of Care	Action
Symptomatic Care^b	
 • Pruritic lesions: Cool compresses and oral antihistamine therapies. • Fissuring lesions: Monsel's solution, silver nitrate, or zinc oxide cream. • Desquamation: Thick emollients and mild soap. • Paronychia: Antiseptic bath, local potent corticosteroids in addition to antibiotics; if no improvement, consult dermatologist or surgeon. • Infected lesions: Appropriate bacterial/fungal culture-driven systemic or topical antibiotics.

^a Rash prophylaxis is recommended for the first 6 weeks of study treatment.

^b Patients who develop rash/skin toxicities should be seen by a qualified physician and should receive evaluation for symptomatic/supportive care management.

Trametinib Dose Modification Guidelines and Management for Rash Deemed Related to Trametinib		
Rash Severity	Management Guideline	Dose Modification
Grade 1	
 • Initiate prophylactic and symptomatic treatment measures.¹ • Use moderate strength topical steroid.² 	
 • Continue trametinib.
Grade 2	
 • Initiate prophylactic and symptomatic treatment measures.¹ • Use moderate strength topical steroid.² • Reassess after 2 weeks. 	
 • Continue trametinib. • If the rash is intolerable, trametinib may be interrupted until recovery to \leq grade 1 or continued at a one dose level reduction after discussion with the MSK Principal Investigator. • If trametinib is interrupted, once rash recovers to \leq grade 1, trametinib may be restarted at the original dose or at a one dose level reduction. • If trametinib was continued at a one dose level without treatment interruption and the rash recovers to \leq grade 1 within 2 weeks, increasing the dose to previous dose level is permitted.
Grade ≥ 3	
 • Use moderate strength topical steroids PLUS oral methylprednisolone dose pack.² • Consult dermatologist. 	
 • Interrupt trametinib until rash recovers to \leq grade 1*. • Restart with trametinib at the original dose or reduced by one dose level.^{3,4} • If no recovery to \leq grade 2 within 4 weeks, permanently discontinue trametinib.

1. Rash prophylaxis is recommended for the first 6 weeks of study treatment.

2. Moderate-strength topical steroids: Hydrocortisone 2.5% cream or fluticasone propionate 0.5% cream

3. Approval of CTEP Medical Monitor is required to restart study treatment after >4 weeks of interruption.

4. Trametinib may be escalated to previous dose level if no rash is evident 4 weeks after restarting study treatment.

* If grade 3 rash develops without optimal supportive care management and is considered tolerable, the treating physician may elect to continue trametinib while initiating optimal supportive care management.

6.1.3 Trametinib Dose Modifications for Visual Changes

Trametinib is known to be associated with visual adverse events. An ophthalmologist should be consulted if changes in vision develop. However, if the visual changes are clearly unrelated to

study treatment (e.g., allergic conjunctivitis), then monitor closely as it may be reasonable to defer ophthalmic examination. Special attention should be given to retinal findings (e.g., retinal pigment epithelial detachment (RPED) or retinovascular abnormalities (*i.e.*, branch or central retinal vein occlusions [RVO]). For events of visual changes regardless of severity but for which an ophthalmic examination is conducted, a blood sample for PK analysis is encouraged when feasible, and the blood sample should be drawn as close as possible to the time of the event.

The ophthalmology exam will include best corrected visual acuity, visual field examination, tonometry, slit lamp biomicroscopic examination, and indirect fundoscopy. Optical coherence tomography is recommended at scheduled visits and if retinal abnormalities are suspected. Other types of ancillary testing including visual field examination, fundus photography, and fluorescein angiography may also be indicated as determined by clinical exam.

Guidelines regarding event management and dose reduction for visual changes considered to be related to study treatment are provided in the table below.

Management and Trametinib Dose Modification for Visual Changes and/or Ophthalmic Examination Findings		
Event CTCAE Grade	Management Guideline	Dose Modification
Grade 1*	
 Consult ophthalmologist within 7 days of onset. 	
 If dilated fundus examination cannot be performed within 7 days of onset, hold trametinib until RPED and RVO can be excluded by retina specialist/ophthalmologist. If RPED and RVO excluded, continue/or restart trametinib at same dose level. If RPED suspected/diagnosed: See RPED dose modification table below (following this table); report as SAE. If RVO diagnosed: Permanently discontinue trametinib and report as SAE.
Grade 2 and Grade 3	
 Consult ophthalmologist immediately. 	
 Hold trametinib If RPED or RVO excluded, restart trametinib at same dose level after visual AE is \leq grade 1. If no recovery within 3 weeks, discontinue trametinib If RPED diagnosed: See RPED dose modification table below; report as SAE. If RVO: Permanently discontinue trametinib and report as SAE.
Grade 4	
 Consult ophthalmologist immediately. Report as SAE. 	
 Hold Trametinib If RPED/RVO excluded, may restart trametinib at same or reduced dose after discussion with the CTEP Medical Monitor. If RVO or RPED, permanently discontinue trametinib.

Abbreviations: RPED = retinal pigment epithelial detachments; RVO = retinal vein occlusion; SAE = serious adverse event

*If visual changes are clearly unrelated to study treatment (e.g., allergic conjunctivitis), monitor closely but ophthalmic examination is not required.

Trametinib Dose Modification for RPED	
Event CTCAE Grade	Action and Dose Modification
Grade 1 RPED (Asymptomatic; clinical or diagnostic observations only)	
 Continue treatment with retinal evaluation monthly until resolution. If RPED worsens, follow instructions below.
Grade 2-3 RPED (Symptomatic with mild to moderate decrease in visual acuity; limiting instrumental ADL)	
 Interrupt trametinib. Retinal evaluation monthly. If improved to \leq Grade 1, restart trametinib with one dose level reduction (reduced by 0.5 mg) or discontinue in patients taking trametinib 1 mg daily. If no recovery within 4 weeks permanently discontinue trametinib

6.1.4 Trametinib Dose Modification for Diarrhea

Episodes of diarrhea have occurred in patients receiving trametinib (Investigator's Brochure, 2012a). Other frequent causes of diarrhea may include concomitant medications (e.g., stool softeners, laxatives, antacids, etc.), infections by *C. difficile* or other pathogens, or partial bowel obstruction. Those conditions should be excluded.

Guidelines regarding management and dose modification for diarrhea considered related to trametinib are provided in the [table](#) below.

Management and Trametinib Dose Modification Guidelines for Diarrhea Deemed Related to Trametinib		
CTCAE Grade	Adverse Event Management	Action and Dose Modification
Uncomplicated Diarrhea,¹ Grade 1 or 2	
 Diet: Stop all lactose containing products; eat small meals, BRAT-diet (banana, rice, apples, toast) recommended. Hydration: 8-10 large glasses of clear liquids per day (e.g., Gatorade or broth). Loperamide³: Initially 4 mg, followed by 2 mg every 4 hours or after every unformed stool; maximum 16 mg/day. Continue until diarrhea-free for 12 hours. Diarrhea >24 hours: Loperamide 2 mg every 2 hours; maximum 16 mg/day. Consider adding oral antibiotics. Diarrhea >48 hours: Loperamide 2 mg every 2 hours; maximum 16 mg/day. Add budesonide or other second-line therapies (otreotide, or tincture of opium) and oral antibiotics. 	
 Continue trametinib. If diarrhea is grade 2 and intolerable, interrupt trametinib until diarrhea resolves to grade \leq1. If there is an interruption in dosing, trametinib can be continued at the same dose level when treatment is restarted.

Management and Trametinib Dose Modification Guidelines for Diarrhea Deemed Related to Trametinib		
CTCAE Grade	Adverse Event Management	Action and Dose Modification
Uncomplicated Diarrhea,¹ Grade 3 or 4	
 Clinical evaluation mandatory. Loperamide³: Initially 4 mg, followed by 2 mg every 4 hours or after every unformed stool; maximum 16 mg/day. Continue until diarrhea-free for 12 hours. Oral antibiotics and second-line therapies if clinically indicated Hydration: Intravenous fluids if clinically indicated. Antibiotics (oral or intravenous) if clinically indicated. Intervention should be continued until the subject is diarrhea-free for ≥ 24 hours. Intervention may require hospitalization for subjects at risk of life-threatening complications. 	
 Interrupt trametinib until diarrhea resolves to \leq grade 1. Restart with trametinib reduced by one dose level.⁴ If 3 dose reductions of study treatment are clinically indicated, permanently discontinue trametinib. If treatment delay is > 21 days, discontinue trametinib.
Any Complicated Diarrhea²		

1. **Uncomplicated diarrhea** defined by the absence of symptoms such as vomiting \geq grade 2, pyrexia, sepsis, neutropenia \geq grade 3, frank bleeding, and/or dehydration requiring intravenous fluid substitution (the administration of fluids alone can still be considered ‘uncomplicated diarrhea’ if judged by the investigator as appropriate).

2. **Complicated diarrhea** defined by the presence of symptoms such as vomiting \geq grade 2, pyrexia, sepsis, neutropenia \geq grade 3, frank bleeding, and/or dehydration requiring intravenous fluid substitution (the administration of fluids alone can still be considered ‘uncomplicated diarrhea’ if judged by the investigator as appropriate).

3. Loperamide should be made available prior to start of study treatment so loperamide administration can begin at the first signs of diarrhea.

4. Escalation of trametinib to previous dose level is allowed after consultation with the medical monitor and in the absence of another episode of complicated or severe diarrhea in the 4 weeks subsequent to dose reduction.

6.1.5 Trametinib Dose Modification for Liver Chemistry Changes

Trametinib Dose Modification for Liver Function Test Abnormalities Deemed Related to Trametinib	
Event	Treatment modifications and assessment/monitoring

 ALT ≥ 3x ULN but < 5x ULN and TB < 2x ULN, without symptoms considered related to liver injury or hypersensitivity and who can be monitored weekly for 4 weeks 	
 May continue study drug. Report as SAE if CTEP-AERS reporting criteria is met. If liver chemistry stopping criteria are met any time, proceed as described below. 
MONITORING: Repeat LFT (ALT, AST, ALK, bilirubin) until they return to normal/baseline or stabilise (LFT may be every 2 weeks after 4 weeks if ALT < 3x ULN and TB < 2 ULN).

Trametinib Dose Modification for Liver Function Test Abnormalities Deemed Related to Trametinib	
Event	Treatment modifications and assessment/monitoring

Criteria for discontinuing study drug: When any of the liver stopping criteria below is met, discontinue trametinib
 
 1. ALT $\geq 3 \times$ULN and bilirubin $\geq 2 \times$ ULN or $> 35\%$ direct bilirubin ^{1,2} 2. ALT $\geq 3 \times$ULN and INR > 1.5, if INR measured² (INR threshold does not apply if subject is on anticoagulant) 3. ALT $\geq 5 \times$ ULN 4. ALT $\geq 3 \times$ ULN persists for ≥ 4 weeks 5. ALT $\geq 3 \times$ ULN and cannot be monitored weekly for 4 weeks 6. ALT $\geq 3 \times$ ULN associated with symptoms³ (new or worsening) believed to be related to liver injury or hypersensitivity 	
 • Immediately discontinue study treatment. • Do not restart/rechallenge unless approved by CTEP trametinib medical monitor. / • Report as SAE if: 1) CTEP-AERS reporting criteria are met, or 2) patients meet criteria 1-2. • Perform liver event ASSESSMENT AND WORKUP (see below). • Monitor the subject until liver chemistries resolve, stabilize, or return to baseline (see MONITORING below). / 
MONITORING:
 
In patients stopping for criteria 1-2 (with abnormal TB and INR, indicating potentially more significant liver toxicities):
 
 • Repeat liver chemistries (ALT, AST, ALK, bilirubin) and perform liver event follow-up assessments within 24 hours. • Monitor subjects twice weekly until LFT return to normal/baseline or stabilize. • A specialist or hepatology consultation is recommended. 
In patients stopping for criteria 2-6:
 
 • Repeat LFT and perform liver event follow up assessments within 24-72 hrs • Monitor subjects weekly until LFTs return to normal/baseline or stabilize. 
ASSESSMENT and WORKUP:
 
 • Viral hepatitis serology.⁴ • If possible, obtain blood sample for PK analysis.⁵ • CPK and LDH. • Fractionate bilirubin, if total bilirubin $\geq 2 \times$ ULN. • CBC with differential to assess eosinophilia. • Record clinical symptoms of liver injury, or hypersensitivity on AE CRF. • Record concomitant medications (including acetaminophen, herbal remedies, other over the counter medications). • Record alcohol use. 
Additional work up for patient stopping for criteria 1-2 (with abnormal TB and INR, indicating potentially more significant liver toxicities):
 
 • Anti-nuclear antibody, anti-smooth muscle antibody, Type 1 anti-liver kidney microsomal antibodies, and quantitative total immunoglobulin G (IgG or gamma globulins). • acetaminophen adduct HPLC assay (in subjects with likely acetaminophen use in the preceding). • If there is underlying chronic hepatitis B (e.g. positive hepatitis B surface antigen): quantitative hepatitis B DNA and hepatitis delta antibody.⁶ • Liver imaging (ultrasound, MRI, CT) and /or liver biopsy.

Footnotes:

1 bilirubin fractionation should be performed if testing is available. If bilirubin fractionation testing is unavailable, **record presence of detectable urinary bilirubin on dipstick**, which indicates direct bilirubin elevations and suggesting liver injury.

2. All events of ALT $\geq 3 \times$ ULN **and** bilirubin $\geq 2 \times$ ULN ($> 35\%$ direct bilirubin) or ALT $\geq 3 \times$ ULN **and** INR > 1.5 (if INR measured) may indicate severe liver injury (possible “Hy’s Law”). INR measurement is not required, and the threshold value stated will not apply to subjects receiving anticoagulants.

Trametinib Dose Modification for Liver Function Test Abnormalities Deemed Related to Trametinib	
Event	Treatment modifications and assessment/monitoring
3. New or worsening symptoms believed to be related to liver injury (such as fatigue, nausea, vomiting, right upper quadrant pain or tenderness, or jaundice) or believed to be related to hypersensitivity (such as fever, rash or eosinophilia) 4. Includes: Hepatitis A IgM antibody; Hepatitis B surface antigen and Hepatitis B Core Antibody (IgM); Hepatitis C RNA; Cytomegalovirus IgM antibody; Epstein-Barr viral capsid antigen IgM antibody (or if unavailable, obtain heterophile antibody or monospot testing); Hepatitis E IgM antibody 5. PK sample is desired if feasible. Record the date/time of the PK blood sample draw and the date/time of the last dose of study treatment prior to blood sample draw on the CRF. If the date or time of the last dose is unclear, provide the subject's best approximation. If the date/time of the last dose cannot be approximated OR a PK sample cannot be collected in the time period indicated above, do not obtain a PK sample. 6. If hepatitis delta antibody assay cannot be performed, it can be replaced with a PCR of hepatitis D RNA virus (where needed) (Le Gal et al. , 2005).	

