10. STUDY CALENDAR

Pre-Study and Weeks 1-5 study calendar for all patients:

NOTE FOR THE ^{124}I PET/CT LESIONAL DOSIMETRY: Changes in the scheduling of the tests and/or assessments below, including the first or second ^{124}I PET/CT lesional dosimetry process, may be considered in the event of holidays, scheduling conflicts, unanticipated delays (e.g. delays in ^{124}I shipment, weather, etc...) or interruptions in trametinib therapy after discussion with the Principal Investigator. (NOTE: Week and day number designations may change if there are interruptions in study treatments/assessments.)

	Pre-Study ^f	Wk 1						Wk 2	Wk 3	Wk 4	Wk 5				
		D1	D2	D3	D4	D5	D6 & D7				D1	D2	D3	D4	D5
Trametinib ^a							X	X	X	X	X	X	X	X	X
Adherence to low iodine diet ^b	X ^b	X	X	X	X	X			X ^b	X	X	X	X	X	
Thyrogen ^c		X	X							X	X				
^{124}I administration (approximately 6 mCi) ^d				X								X			
^{124}I PET/CT						X								X	
beta-HCG ^g	X ^g	X ^j								X ^j					
Tumor Genotyping	X ^e														
Informed consent	X														
Demographics	X														
Medical history	X														
Concurrent meds	X	X-----												X	
Physical exam	X					X ^k		X						X ^k	
Vital signs	X					X ^k		X						X ^k	
Height	X														
Weight	X					X ^k		X						X ^k	
Performance status	X					X ^k		X						X ^k	
CBC w/diff, plts	X	X ^k						X		X ^k					
chemistry ^h	X	X ^k						X		X ^k					
PT/aPTT (include INR)	X														
EKG	X														
Echocardiogram or MUGA ^m	X														
Ophthalmology exam ⁿ	X														
Adverse event evaluation		X-----												X	
Radiologic evaluation (CT(s) and/or MRI(s)) for tumor measurements NO IODINATED CONTRAST IS ALLOWED	X														
TSH, free T4, thyroglobulin, thyroglobulin antibody ^l		X	X	X	X	X		X	X	X	X	X	X	X	
Research blood sample ^o	X														
Research biopsy ⁱ	X							X							

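### Section 6.1.5 puts liver stopping criterion 2 (ALT ≥3× ULN with INR >1.5) under two different monitoring schedules; the second heading should read criteria 3–6

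*Combined protocol and SAP*

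**What the plan says.** The table in Section 6.1.5 of the combined protocol and SAP numbers six liver criteria, any one of which stops trametinib. Criterion 1 pairs ALT ≥3× ULN with raised bilirubin. Criterion 2 pairs ALT ≥3× ULN with "INR > 1.5, if INR measured". Criteria 3 to 6 rest on ALT level, its persistence, inability to monitor weekly, or associated symptoms.

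The monitoring text then has two blocks:

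- The first is headed "In patients stopping for criteria 1-2 (with abnormal TB and INR, indicating potentially more significant liver toxicities". It asks staff to repeat liver chemistries and "perform liver event follow-up assessments within 24 hours", to monitor twice weekly, and recommends a specialist or hepatology consultation.
- The second is headed "In patients stopping for criteria 2-6". It asks for repeat tests and follow-up at 24–72 hours and weekly monitoring, and has no consultation line.

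Elsewhere in the same table the SAE rule reads "Report as SAE if: 1) CTEP-AERS reporting criteria are met, or 2) patients meet criteria 1-2", and the extended work-up is headed "Additional work up for patient stopping for criteria 1-2". Footnote 2 describes both the bilirubin and the INR combinations as possibly indicating severe liver injury (possible Hy's Law). It adds that "INR measurement is not required, and the threshold value stated will not apply to subjects receiving anticoagulants".

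**The concern.** Criterion 2 is named in both monitoring headings, and the instructions beneath them differ in timing, in frequency and on consultation. No other part of the protocol gives an order of precedence. This is current protocol text, and the criteria list and both headings are intact.

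The event affected is one that footnote 2 treats as potentially serious, so it should have a single follow-up schedule. Staff who work from the second heading could retest later, monitor less often and not see the consultation recommendation, and could still point to protocol text in support.

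**Working it through.** The plan gives no figure to reproduce. The check compares the two groupings as sets, compares what each block requires, and looks at every other place in the table where the criteria are grouped.

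**Step 1. Overlap.** The first heading covers {1, 2} and the second {2, 3, 4, 5, 6}. They share exactly one element, criterion 2.

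**Step 2. What criterion 2 attracts under each heading.**

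| Item | First block (1–2) | Second block (2–6) |
|---|---|---|
| Repeat tests and follow-up | within 24 h | 24–72 h |
| Monitoring | twice weekly | weekly |
| Specialist or hepatology consultation | recommended | not mentioned |

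Largest difference in the first repeat test: 72 h − 24 h = 48 h. Monitoring visits over 4 weeks (an illustrative window, since the protocol sets none): 2 × 4 = 8 under the first block and 1 × 4 = 4 under the second.

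**Step 3. Which heading is wrong.** The first monitoring heading is one side of the conflict, so it is set aside as a vote. Three other places remain, and all put criterion 2 with criterion 1:

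1. The SAE rule.
2. The additional work-up heading, which carries the same gloss about abnormal bilirubin and INR as the first monitoring heading. INR appears only in criterion 2, so the gloss has to include that criterion.
3. Footnote 2, whose marker is attached to criteria 1 and 2 and which treats them alike.

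The second monitoring heading is the only place that groups criterion 2 with criteria 3–6.

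**Step 4. Candidate repairs.** Reading the second heading as 3–6 gives {1, 2} and {3, 4, 5, 6}: no overlap, and all six criteria covered once. The alternative is to cut the first heading to criterion 1 alone. That contradicts its own gloss and separates monitoring from the SAE and work-up groupings.

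**Step 5. Exposure.** Section 13.2 plans 25 + 10 = 35 patients in Cohorts A and B; Section 13.1 allows replacements, so slightly more could be treated. In Section 10 the row "PT/aPTT (include INR" is marked only at the pre-study visit, and neither later calendar includes it. INR is also absent from the repeat-chemistry and work-up lists in Section 6.1.5. Criterion 2 can therefore be met on treatment only through an unscheduled INR in a patient not on an anticoagulant.

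**Step 6. Patients meeting more than one criterion.** ALT ≥5× ULN with INR >1.5 meets criteria 2 and 3. ALT ≥5× ULN with bilirubin ≥2× ULN meets criteria 1 and 3. Both patients stay under two headings even after renumbering.

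**The case against.** The strongest reply is that the two blocks can be followed together. A retest at 24 hours satisfies both, twice-weekly monitoring includes weekly monitoring, and the consultation is only recommended. A careful reader would apply the stricter block, which comes first and is explicitly labelled as the more serious case. On that view the 48-hour and 8-versus-4 figures describe an unlikely misreading. This is largely right, and it is why the point is minor. It does not remove the overlap: the protocol never states that the stricter schedule prevails, and a safety table should not leave that to inference.

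A second reply is that 3–6 is an inference, because the protocol prints no corrected range. That is true. The inference still rests on three places outside the disputed pair of headings, and the alternative repair conflicts with all three.

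A third is that renumbering separates the labels but not every patient, as Step 6 shows. That stands, and it is a reason to add a precedence clause alongside the new number.

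**Conclusion.** The inconsistency is real and the second monitoring heading is the error. Its effect is confined to follow-up after trametinib is stopped for criterion 2: a first retest up to 48 hours later and half the monitoring visits, if staff use the wrong block. The rules on stopping, rechallenge, SAE reporting and work-up for that criterion do not conflict. Few if any patients are likely to be affected, given the planned numbers and the absence of scheduled on-treatment INR. Endpoints, sample size and error rates do not change. This is a minor correction to an operative safety rule. The conclusion assumes that the grouping used in the SAE rule, the work-up heading and footnote 2 is the intended one.

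**What to change.** In the next amendment, renumber the second monitoring heading in Section 6.1.5 to *criteria 3–6*, so that criterion 2 follows only the 24-hour, twice-weekly schedule. Preferably add *and not meeting criteria 1–2* to the same heading, which settles the case of a patient who meets criteria from both groups. Until then, tell staff to apply the first block to criterion 2.

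The cost is one digit, plus a short phrase if the clause is added. No new assessment is created, because the stricter schedule already names criterion 2.
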